5.2. Exclusion Criteria

Participants are excluded from the study if any of the following criteria apply:

Medical Conditions

1. Other medical or psychiatric condition, including recent (within the past year) or active suicidal ideation or behavior, or laboratory abnormality that may increase the risk of study participation or, in the investigator's judgment, make the participant inappropriate for the study. Any psychiatric condition including recent or active suicidal ideation or behavior that meets any of the following criteria:
 - a. Suicidal ideation associated with actual intent and a method or plan in the past year: "Yes" answers on items 4 or 5 of the Columbia Suicide Severity Rating Scale (C-SSRS) (Section 8.2.11).
 - b. Suicidal behavior in the past year: a "Yes" answer on any question in the suicidal behavior section of the C-SSRS.
 - c. For participants who had previous history of suicidal behaviors in the past >1 year: (a "Yes" answer to any of the suicidal behavior items of the C-SSRS), a risk assessment must be performed and documented by a qualified mental health

professional to assess whether it is safe for the participant to participate in the trial.

- d. The presence of any current major psychiatric disorder that is not explicitly permitted in the inclusion/exclusion criteria.
- e. Clinically significant depression as indicated by a Patient Health Questionnaire-8 Items (PHQ-8) total score ≥ 15 ([Section 8.2.12](#)).

NOTE: For any participant who has significant depression or any suicidal behavior, the participant will not be assigned to study intervention and should be referred for appropriate evaluation and treatment.

- 2. Any current hearing loss or current disease that can affect hearing, including disorders associated with progressive hearing loss in adults, e.g. Meniere's disease, otosclerosis, superior semicircular canal dehiscence or labyrinthitis.
- 3. Occupational or recreational noise exposure sufficient to place the participant at risk for noise-induced hearing loss without proper ear protection as determined by the audiology professional performing the screening audiological evaluation.
- 4. Current or history of clinically significant central or peripheral neurological disease regardless of etiology or any other neurologic disease that could impact study results in the judgement of the investigator or the examining neurologist.
- 5. First degree family history of hereditary neuropathy.

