8.2.11. Suicidal Ideation and Behavior Risk Monitoring

8.2.11.1. Columbia Suicide Severity Rating Scale (C-SSRS)

There are 2 versions of the C-SSRS to be utilized in this study - “C-SSRS for screening and Day 1 visits” and “C-SSRS for any visits after Day 1”⁽⁵⁴⁾. The version used is dictated by the actual study visit and the participant population (See the SoA [Section 1.3]).

At the screening or Day 1 visits, if the participant has had suicidal ideation associated with actual intent and a method or plan in the past year (“yes” answers on items 4, 5), the participant will not be included in the study. For participants, suicidal behavior in the past year (“Yes” answer on any question in the suicidal behavior section of the C-SSRS), is exclusionary. For participants who have had previous history of suicidal behaviors in the past >1 year, (a “Yes” answer to any of the suicidal behavior items of the C-SSRS), a risk assessment must be performed and documented by a qualified mental health professional to assess whether it is safe for the participant to participate in the trial.

Any participants who are not eligible due to suicidal ideation or behavior should be referred for appropriate evaluation and treatment.

For all participants with suicidal ideation associated with actual intent and a method or plan in the past year: At any visits after Day 1, if there are “yes” answers on items 4, 5, or on any question in the suicidal behavior section of the C-SSRS, the participant will be discontinued from the study and referred to a mental health professional for appropriate evaluation and treatment or immediately referred to the Emergency Room at the investigator’s judgement.

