10.9.2. Telehealth Visits

In the event that in-clinic study visits cannot be conducted, every effort should be made to follow up on the safety of study participants at scheduled visits per the SoA (Section 1.3) or unplanned visits. Telehealth visits may be used to continue to assess participant safety and collect data points. Telehealth includes the exchange of healthcare information and services via telecommunication technologies (eg, audio, video, video-conferencing software) remotely, allowing the participant and the investigator to communicate on aspects of clinical care, including medical advice, reminders, education, and safety monitoring. The following assessments must be performed during a telehealth visit:

- Review dosing logs and record investigational product, including doses taken and any interruptions in intake of investigational product (ie, missed doses) since the last contact, and calculate compliance.
- Review and record any AEs and SAEs since the last contact. Refer to [Section 8.3](#).
- Review and record any new concomitant medications or changes in concomitant medications since the last contact.
- For WOCBP: Review and record contraceptive method and results of pregnancy testing. Confirm that the participant is adhering to the contraception method(s) required in the protocol. Refer to [Appendix 4](#) and [Section 10.9.3.1](#) of this appendix regarding pregnancy tests and to [Section 5.3.1](#) of this protocol regarding contraception checks.
- Body temperature and collection method (eg, oral, tympanic, axillary), pulse rate, and respiratory rate (measured by study participant/caregiver).
- Collection of interim audiological history (using Part 1 in the Audiometry Guide Worksheet for Post Day 1 visits) at visits requiring audiological evaluation with entry of clinically significant changes onto the AE section of the eCRF, as appropriate.
- Collection of interim neurological history (using General Neurology and Neuropathy Assessment Completion Guidelines) must be obtained, with entry of clinically significant changes onto the AE section of the eCRF, as appropriate.
- Administration of the C-SSRS performed by a qualified rater. As per [Section 8.2.11.1](#), if there are “yes” answers on items 4 or 5 of the suicidal ideation section or on any question in the suicidal behavior section of the C-SSRS, the participant will be discontinued from the study and referred to a mental health professional for appropriate evaluation and treatment.

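### Exclusion 1 contradicts itself on suicidal behavior more than a year ago, and the on-study suicidality rule covers different participants in Sections 8.2.11.1 and 10.9.2

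*Protocol*

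**What the plan says.** **Entry.** Exclusion 1 in Protocol Section 5.2 opens with a time frame, "including recent (within the past year) or active suicidal ideation or behavior". Item 1a excludes for "Suicidal ideation associated with actual intent and a method or plan in the past year" and item 1b for "Suicidal behavior in the past year". Item 1c deals with older events: "For participants who had previous history of suicidal behaviors in the past >1 year", a mental health professional must carry out and document a risk assessment. Section 8.2.11.1 repeats that route and gives its purpose, "to assess whether it is safe for the participant to participate in the trial". The note at the end of criterion 1 then reads: "For any participant who has significant depression or any suicidal behavior, the participant will not be assigned to study intervention". The corresponding referral sentence in 8.2.11.1 is narrower and speaks only of people who are already ineligible.

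**On study.** The rule for later visits in 8.2.11.1 begins "For all participants with suicidal ideation associated with actual intent and a method or plan in the past year: At any visits" after Day 1. It then requires discontinuation and referral if item 4, item 5 or any suicidal behavior question is answered yes. Section 10.7.2 uses the same description of ideation, followed by a colon and the same C-SSRS answers. Section 10.9.2, for telehealth visits, attributes its rule to 8.2.11.1 but has no opening condition. A yes on item 4 or 5, "or on any question in the suicidal behavior section of the C-SSRS, the participant will be discontinued from the study".

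Sections 5 and 8 rule out waivers and exemptions.

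**The concern.** Both passages are participant-safety rules that sites must apply without exceptions. At entry, two sites that each follow the written text can reach opposite decisions about the same cleared person, and either decision can be called a deviation from the other sentence. After Day 1, whether discontinuation is mandatory can depend on whether the same C-SSRS answer is given in the clinic or by telehealth.

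For the data, the reach is small. It touches eligibility deviations, disposition and the count of discontinuations. It does not touch the BAEP endpoint or the precision calculation.

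**Working it through.** No arithmetic decides this point. The check sets the passages side by side and runs test cases through them.

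**Entry case.** Suicidal behavior three years before screening, none since; no past-year ideation on C-SSRS items 4 or 5; PHQ-8 total below 15; favorable risk assessment.

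- 1a, 1b and 1e (the PHQ-8 item): not met.
- 1c and 8.2.11.1: the assessment has been done and is favorable, so entry is open. Asking whether participation is safe has a purpose only if some of these people may take part.
- Closing note: behavior of any date suffices, so the person is not assigned treatment.

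The last two results conflict.

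**On-study cases.** The phrase about the past year in 8.2.11.1 has no stated anchor, so both anchors are tried. Section 10.7.2 can be read with the phrase as a condition or as a label for the answers that follow.

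| Answer at a visit after Day 1 | 8.2.11.1, year counted back from entry | 8.2.11.1, year counted back from the visit | 10.7.2 | 10.9.2 (telehealth) |
|---|---|---|---|---|
| New yes on item 4 or 5 | Opening condition not met by anyone properly enrolled | Met: discontinue | As 8.2.11.1 if a condition; discontinue if a label | Discontinue |
| Yes on a behavior question, no ideation with intent and a method or plan | Not met | Not met | Not met if a condition; discontinue if a label | Discontinue |

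The first row depends on the anchor. If the year is counted back from the visit, then from about Month 12 of up to 60 months of dosing (Section 4.3) the look-back year lies wholly on study. The second row does not depend on the anchor: the behavior answer is a listed trigger, yet the opening words of 8.2.11.1 do not reach the person who gives it. That row is the firm finding.

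**Where it can arise.** The schedules in Section 1.3.2 list the C-SSRS at all 9 visits from Month 1 to Month 15E and at all 6 TP3 visits, so up to 9 + 6 = 15 scheduled assessments after Day 1, plus early termination. Section 10.9.6 bars the C-SSRS at home visits, so the contrast is between on-site and telehealth visits. Telehealth visits apply only while the public-emergency appendix is in force.

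**Is recruitment over?** Section 4.4 defines the primary completion date by the last participant's Month 9 visit. SAP version 4.0, dated 17 August 2022, describes analyses already added to the report on that milestone. Nine months before 17 August 2022 is mid-November 2021, so the last participant would have started by about then. That is before Amendment 2, which the SAP dates 28 April 2022. This is an inference: neither document states when enrolment closed.

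**The case against.** On entry, the best defense is that the specific provision governs the general one. Criterion 1 opens with recent or active suicidality, the note is in the present tense and is tied to referral, and applying it to old events would leave 1c with no function. That is a workable guess at the intent. It stands only as a guess, because the note names suicidal behavior of any kind without a limit or an exception for people cleared under 1c. The parallel sentence in 8.2.11.1 shows that a limited wording was available.

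A reader might go further and infer that 1c itself excludes, because it sits in a list of excluding conditions. The text does not support this: 1c describes an assessment to be done, and 8.2.11.1 confirms that its result decides.

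On study, the defense is stronger. In 10.7.2 the ideation phrase can be a label followed by its triggers, which is how 1a is laid out, so that a behavior answer alone suffices. In 8.2.11.1 the reference to the behavior questions would be largely idle if behavior alone never counted. Section 10.9.2 presents the unrestricted rule as the content of 8.2.11.1. All this suggests that every participant was meant to be covered, but it does not remove the restricting words from 8.2.11.1.

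A reader might also infer that suicidal behavior found on site is left unmanaged. The protocol does not support that. Section 10.7 lets the investigator withdraw a participant at any time, 10.7.2 covers treatment-related SAEs and, by discretion, other serious or severe events, and Section 8 sends safety issues to the sponsor at once. What remains is the difference between a mandatory rule and a discretionary one.

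**Conclusion.** The point holds as an internal contradiction in a safety rule and should be corrected.

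1. The closing note conflicts with 1c and 8.2.11.1 for anyone cleared after a risk assessment. Entry under 1c is conditional, not automatic.
2. Read literally, 8.2.11.1 does not reach on-study suicidal behavior without ideation with intent and a method or plan, while 10.9.2 does. Section 10.7.2 is open to either reading.

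It is tempting to infer that the on-study rule covers only people whom 1a already keeps out, and so nobody enrolled. That follows only if the past year is fixed at entry. No passage fixes it there, and counting back from the visit brings new ideation within the rule.

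The size is textual. The documents do not say how many screened people had older suicidal behavior or how often the on-study case would occur, so no count is offered. The on-study part is the live one while the C-SSRS continues through TP3. If recruitment is complete, as the SAP history suggests, the entry part matters mainly for judging whether past enrolments were deviations, and for any reuse of the text. Which version of criterion 1 applied at each enrolment would have to be checked. The sample size and the primary analysis are unaffected.

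**What to change.** The sponsor should reconcile two sets of passages:

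- The note closing exclusion 1 with item 1c and Section 8.2.11.1, so that suicidal behavior more than a year before entry has one stated disposition.
- The opening words of the on-study rule in 8.2.11.1 and 10.7.2 with Section 10.9.2, so that all three say the same about who is covered, whatever the visit type. If a past-year phrase remains, it should say from which date the year is counted.

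The sponsor decides which rule stands; this review takes no position on that. The cost is the wording of a few sentences and a clarification letter to sites. No assessment, visit or analysis is added. If recruitment is confirmed as closed, a short file note on how past cases under 1c were handled would settle the entry part.

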5.3. Lifestyle Considerations

5.3.1. Contraception

Participants who are WOCBP must agree to use one highly effective method of contraception (as specified in Section 10.4), as applicable.

The investigator or his/her designee, in consultation with the participant, will confirm that the participant has selected an appropriate method of contraception for the individual participant from the permitted list of contraception methods (See Section 10.4), and will confirm that the participant has been instructed in its consistent and correct use. At time points indicated in the SoA (Section 1.3), the investigator or designee will inform the participant of the need to use highly effective contraception consistently and correctly and document the conversation and the participant's affirmation in the participant's chart (participants need to affirm their consistent and correct use of at least 1 of the selected methods of contraception). In addition, the investigator or designee will instruct the participant to call immediately if the selected contraception method is discontinued and document the requirement to use an alternate protocol-specified method, including if the participant will no longer use abstinence as the selected contraception method or if pregnancy is known or suspected in the participant or partner. The contraception check for WOCBP will be performed during each study visit and monthly between study visits at the time of the phone contact to check the at-home pregnancy test results (see Section 8.2.13).

5.3.2. Meals and Dietary Restrictions

On study visit days when lipid panel will be collected (see the SoA [Section 1.3]), participants must comply with fasting requirements for at least 8 hours prior to the visit. Water and permitted non-study medications are allowed (see Section 6.5.1).

Participants must agree not to drink tonic water during the study.

5.3.3. Caffeine and Tobacco

Participants will abstain from using tobacco products or ingesting caffeine- or xanthine- containing products (eg, coffee, tea, cola drinks, and chocolate) for at least 30 minutes before pulse rate and blood pressure measurements.

5.3.4. Elective Surgery

During the study, no elective surgery should occur without first consulting with the sponsor. Preferably, elective surgery should occur before the study or be delayed until participation in

the study is completed. Participants who require elective surgery should temporarily discontinue study intervention for one week prior to the surgical procedure and remain off study intervention after the surgical procedure until sutures/staples are removed. If absorbing sutures or chemical closure methods are utilized, study intervention can be resumed when the operative site is sufficiently healed, and risk of infection is minimal. Per [Section 6.4](#), if the participant interrupts study intervention for >14 consecutive days, this must be discussed with the sponsor for possible withdrawal from the study. Refer to [Section 6.5.4](#) for additional guidance regarding surgeries.

5.4. Screen Failures

Screen failures are defined as participants who consent to participate in the clinical study but are not subsequently randomly assigned to study intervention. A minimal set of screen failure information is required to ensure transparent reporting of screen failure participants to meet the Consolidated Standards of Reporting Trials (CONSORT) publishing requirements and to respond to queries from regulatory authorities. Minimal information includes demography, screen failure details, eligibility criteria, and any serious adverse event (SAE).

Screening laboratory tests with abnormal results may be repeated to confirm abnormal results (with the same screening number); the last value will be used to determine eligibility. If results return to normal within the 5-week screening period, the participant may enter the study upon discussion with, and agreement by, the sponsor.

Participants who do not meet the criteria for participation in this study (screen failure) may be rescreened (with a new screening number) following an agreement with the sponsor.

6. STUDY INTERVENTION

Study intervention is defined as any investigational intervention(s), marketed product(s), placebo, medical device(s), or study procedure(s) intended to be administered to a study participant according to the study protocol.

6.1. Study Intervention(s) Administered

In both the placebo-controlled phase (TP1) and active therapy extension phase (TP2), each participant will receive a total of 4 tablets QD during the initial 4-week period and a total of 1 tablet QD during the remainder of that study phase. To maintain blinding, participants who received PF-06651600 during the placebo-controlled phase will receive 1 tablet QD of PF-06651600 and 3 tablets of placebo QD for a total of 4 tablets QD during the initial 4-week period of the active therapy extension phase.

Placebo-Controlled Phase (TP1) by Dose Period				
Arm Name	PF-06651600		Placebo	
	Visits 2 – 3	Visits 3 - 6	Visits 2 – 3	Visits 3 - 6
	PF-06651600 200 mg QD (4-week dose)	PF-06651600 50 mg QD	Placebo (4-week dose)	Placebo
Intervention Number	PF-06651600	PF-06651600	Not applicable	Not applicable
Intervention Name	Ritlecitinib	Ritlecitinib	Placebo	Placebo
Type	Small molecule	Small molecule	Other	Other
Dosage Form	Tablet	Tablet	Tablets	Tablets
Dose Strength	50 mg	50 mg	0 mg	0 mg
Dosage	50 mg – 4 tablets	50 mg – 1 tablet	0 mg -4 tablets	0 mg -1 tablet
Route of Administration	Oral	Oral	Oral	Oral
Sourcing	Provided centrally by the Sponsor	Provided centrally by the Sponsor	Provided centrally by the Sponsor	Provided centrally by the Sponsor
Packaging and Labeling	Study Intervention will be provided in blister cards. Each blister card will be labeled as required per country requirement.	Study Intervention will be provided in blister cards. Each blister card will be labeled as required per country requirement.	Study Intervention will be provided in blister cards. Each blister card will be labeled as required per country requirement.	Study Intervention will be provided in blister cards. Each blister card will be labeled as required per country requirement.

Active Therapy Extension Phase (TP2) & Extension Phase (TP3)				
	Initial 4-Weeks Dose (4 Tablets)			50 mg QD Dose (1 Tablet/Capsule) (All Participants)
	Received Placebo in Placebo-Controlled Phase	Received PF-06651600 in Placebo-Controlled Phase		
ARM Name	PF-06651600 200 mg QD	PF-06551600 50 mg QD/Placebo		PF-06551600 50 mg QD
Intervention Number	PF-06651600	PF-06651600	Not applicable	PF-06651600
Intervention Name	Ritlecitinib	Ritlecitinib	Placebo	Ritlecitinib
Type	Small molecule	Small molecule	Other	Small molecule
Dosage Form	Tablet	Tablet	Tablet	Tablet/Capsule
Dose Strength	50 mg	50 mg	0 mg	50 mg
Dosage	50 mg – 4 tablets	50 mg – 1 tablet	0 mg - 3 tablets	50 mg – 1 tablet or capsule (TP3 only)
Route of Administration	Oral	Oral	Oral	Oral
Sourcing	Provided centrally by the Sponsor	Provided centrally by the Sponsor	Provided centrally by the Sponsor	Provided centrally by the Sponsor
Packaging and Labeling	Study Intervention will be provided in blister cards. Each blister card will be	Study Intervention will be provided in blister cards. Each	Study Intervention will be	Study Intervention will be provided in blister cards or

Active Therapy Extension Phase (TP2) & Extension Phase (TP3)				
	Initial 4-Weeks Dose (4 Tablets)			50 mg QD Dose (1 Tablet/Capsule) (All Participants)
	Received Placebo in Placebo-Controlled Phase	Received PF-06651600 in Placebo- Controlled Phase		
	labeled as required per country requirement.	blister card will be labeled as required per country requirement.	provided in blister cards. Each blister card will be labeled as required per country requirement.	bottles (TP3 only). Each blister card/bottle will be labeled as required per country requirement.

Abbreviation: QD = once daily

Participants will swallow the study intervention whole and will not manipulate or chew the study intervention prior to swallowing.

6.2. Preparation/Handling/Storage/Accountability

- The study intervention will be dispensed using an Interactive Response Technology (IRT) management system at each visit as specified in the SoA ([Section 1.3](#)). At the Month 1 visit, the participant will return the package containing the study intervention which was dispensed at the Day 1 visit for accountability.
- A qualified staff member will dispense the study intervention via unique container numbers on the blister cards or bottles (TP3 only) provided. The participant should be instructed to maintain the product in the blister cards or bottles provided throughout the course of dosing and return the blister cards or bottles to the site at the next study visit. Site staff will instruct participants on the proper storage requirements for study intervention that is taken home.
- The investigator or designee must confirm appropriate temperature conditions have been maintained during transit for all study intervention received and any discrepancies are reported and resolved before use of the study intervention.

Only participants enrolled in the study may receive study intervention and only authorized site staff may supply or administer study intervention. All study intervention must be stored in a secure, environmentally controlled, and monitored (manual or automated) area in accordance with the labeled storage conditions with access limited to the investigator and authorized site staff. At a minimum, daily minimum and maximum temperatures for all site storage locations must be documented and available upon request. Data for nonworking days must indicate the minimum and maximum temperatures since previously documented for all site storage locations upon return to business.

Any excursions from the study intervention label storage conditions should be reported to Pfizer upon discovery along with any actions taken. The site should

actively pursue options for returning the study intervention to the storage conditions described in the labeling, as soon as possible. Once an excursion is identified, the study intervention must be quarantined and not used until Pfizer provides permission to use the study intervention. Specific details regarding the definition of an excursion and information the site should report for each excursion will be provided to the site in the IP Manual.

Study interventions should be stored in their original containers.

Site staff will instruct participants on the proper storage requirements for take-home study intervention.

The investigator, institution, or the head of the medical institution (where applicable) is responsible for study intervention accountability, reconciliation, and record maintenance (ie, receipt, reconciliation, and final disposition records), such as the Investigational Product Accountability Log or sponsor-approved equivalent. All study interventions will be accounted for using a study intervention accountability form/record. All study intervention that is taken home by the participant, both used and unused, must be returned to the investigator by the participant. Returned study intervention must not be redispensed to the participants.

Further guidance and information for the final disposition of unused study interventions are provided in the IP Manual. All destruction must be adequately documented. If destruction is authorized to take place at the investigator site, the investigator must ensure that the materials are destroyed in compliance with applicable environmental regulations, institutional policy, and any special instructions provided by Pfizer.

Upon identification of a product complaint, notify the sponsor within 1 business day of discovery as described in the IP Manual.

